6.2 Data Security

Clinical data for participants will be stored in REDCap. REDCap is a secure, web-based application. The server is located at Rutgers University and data is stored on secure networks behind a managed firewall. Data abstractors and clinical investigators will be the only ones who access to identified dataset. Other study members will only have access to data in aggregate or de-identified datasets. Signed IC will be kept inside the locked cabinet

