1.3 Research Design and Methods

Implement povidone-iodine (10%) pre-operative nasal decolonization for patients undergoing same-day surgery and evaluate efficacy and tolerability of this intervention in eradicating nasal colonization.

HRP-503a - TEMPLATE - Interventional Research Protocol 1.1.21 Protocol Title: Povidone-lodine for nasal decolonization

A. Research Procedures

This will be a prospective single-blinded randomized placebo-controlled trial of two applications of a nasal 10% PI solution used on the intranasal mucosal surfaces of each nostril in the preoperative holding area within 2 hours prior to surgical incision compared with sterile saline using the same technique. Both the PI and sterile saline will be applied by rotating the swab over the intranasal mucosal surface for 15 seconds; this process will be performed twice for both nostrils, using a new swab for each of the 4 applications. 200 subjects will be chosen from a pool of patients arriving at University Hospital, Newark, NJ for outpatient surgery. Inclusion criteria include community-based patients ages 18-80, ASA 1-3 who will be undergoing an outpatient surgery scheduled for at least 1 hour and up to 6 hours duration. Exclusion criteria include pregnancy, allergy to povidone-iodine, infectious indication for surgery or preexisting known infection/wound, known immunocompromised state, use of antibiotics, chemotherapy, or steroids within 1 month prior to surgery. Additionally, patients presenting for surgeries where field avoidance prevents intraoperative access to the nares (e.g., ENT/OMFS/ophthalmology procedures) will be excluded. Patients will be randomly divided into two groups: control (sterile saline) vs. experimental (PI) This will be done via simple randomization using a computer program that assigns patients as they present into either the control or experimental group while maintaining an overall approximately even ratio of subjects in each group.

B. Data Points

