Potential subjects will be identified from surgical schedule. Patients will be asked for informed consent in the same-day surgery (SDS) unit. They will be given sufficient time to read the IC document and ask questions. While in the preoperative holding area, patients will be asked to sit upright at a 45-90° angle to prevent drainage into the nasopharynx. All patients will first be swabbed for a nasal swab specimen, once in each nostril. Patients will then receive the appropriate nasal applications depending on the group into which they were sorted: Povidone-Iodine or saline. The tolerability assessment of investigating drug will be done with every subject at the Pre-operating room and PACU by a few criteria as burning/itching, pain, irritation, epistaxis, runny nose, and others. Nasal swab specimen will be obtained by the anesthesiologist intraoperatively 1, 2 and 3 hours after investigational drug application as studies have shown that there a significant decrease in colony-forming units of MRSA even within 1-hour post-treatment [9, 10]. These cultures may be intraoperative or postoperative depending on the length of surgery. There will also be a nasal swab specimen obtained while the patient is in the PACU. Study subjects will be stratified according to age, sex, comorbidities, and ethnicity. Additionally, the type of surgery, duration of surgery (Incision start to incision close), number of surgeons present during the procedure (Include all individuals scrubbed in), postoperative hospital stay length, and intraoperative time (patient in OR to patient out OR) will be used in data analysis. The purpose is to identify variables that increase the incidence of surgical site infection.

C. Study Duration

The study will take approximately 2 years, but chart review may continue up to 4 months after the last patient in the study has their procedure. Chart review of subject's postoperative surgical clinic visits will be performed up to 30 days to monitor for any surgical site infection.

D. Endpoints

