The primary study end point is the decrease in S. aureus/MRSA colony forming units (CFU) in nasal swab specimen taken perioperatively after intervention in patients who presented with a positive pre-interventional nasal swab specimen. A secondary endpoint is the presence or absence of surgical site infections at 7 and up to 30-day postop intervals (per retrospective chart review). The review includes an assessment of post-operative infections, complications, and prescribing antibiotics (name, dose, number of days, completing).

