1.7 Drugs/Devices/Biologics

A. Schedule and Administration

Povidone-lodine 10% solution will be given intranasally as a swab with two swabs/nostril for patients in the experimental arm of the study. The control arm will be given sterile saline via the same method.

B. Drug/Device Accountability and Storage Methods

The study drugs will be dispensed by the pharmacy. The study drugs will be administered by study investigators.

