1.9 Data Collection

HRP-503a - TEMPLATE - Interventional Research Protocol 1.1.21 Protocol Title: Povidone-lodine for nasal decolonization

A. Primary Data Collection

[figure not shown]
- **Location**: Data collection will occur in the preoperative holding area, operating rooms, and post-anesthesia care unit of the University Hospital, Newark, NJ.
- **Process of Data Collection**: The investigator who is applying the saline or 10% PI to the study subjects will not be blinded. Nasal cultures will be obtained by the study team members. [name] will be overseeing the entire study.
- Timing and Frequency: There will be swab collections prior to the procedure, at the one-, two-, and three-hour marks after saline or 10% PI is administered.
- Procedures for Audio/Visual Recording: N/A
- Study Instruments: n/a
- Ethnographic Studies, Interviews, Or Observation: N/A
- Subject Identifiers: MRN only

B. Secondary Data Collection

N/A

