2.0 Project Management

2.1 Research Staff and Qualifications

[name] will be available all days of the study. Having worked in this hospital for many years, he is very knowledgeable about the study site, the culture, and the patient population. He will be enlisting the help of study assistants to aid in the collection of data and application of the nasal swabs but will be directly overseeing all of this to ensure everything is in order.

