2.2 Research Staff Training

All involved study team members will be trained how to perform data collection and nasal swab application correctly.

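### Treatment arm is not kept from whoever rates nasal tolerability or abstracts surgical site infection from charts, so arm-aware rating of these two outcomes is possible

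*Combined protocol and SAP*

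**What the plan says.** **Blinding.** Section 1.3 A states: "This will be a prospective single-blinded randomized placebo-controlled trial of two applications of a nasal 10% PI solution". It does not say which party is blinded. Section 1.9 A names one person who is not: "The investigator who is applying the saline or 10% PI to the study subjects will not be blinded". Section 1.7 B adds: "The study drugs will be administered by study investigators".

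**Roles.** Section 2.1 says of the study lead: "He will be enlisting the help of study assistants to aid in the collection of data and application of the nasal swabs". Section 2.2 says: "All involved study team members will be trained how to perform data collection and nasal swab application correctly". Neither section separates the two tasks.

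**Tolerability.** Section 1.3 B says: "The tolerability assessment of investigating drug will be done with every subject at the Pre-operating room and PACU by a few criteria". The criteria include burning or itching, pain, irritation, epistaxis and runny nose. No rater is named, and nothing is said about masking the rater.

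**SSI.** Section 1.3 D makes SSI at 7 and up to 30 days a secondary endpoint, found by looking back through charts. Section 6.4 A gives the source as the electronic record of the patients' visits to their surgeons. On scope, 1.3 D says: "The review includes an assessment of post-operative infections, complications, and prescribing antibiotics (name, dose, number of days, completing". There is no case definition and no masked reader.

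**Data access.** Section 6.2 says: "Data abstractors and clinical investigators will be the only ones who access to identified dataset". Other study members see aggregate or de-identified data. Treatment arm is not mentioned.

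**The concern.** Both outcomes depend on someone's judgement: how a symptom is asked about and written down, or whether a chart entry amounts to an SSI. The team's expectation is on record. Sections 1.1 B and 6.1 expect povidone-iodine to reduce colonization, and 4.7 F mentions a possibly lower SSI risk in that arm. A rater who knows the arm and shares that expectation could, without intending to, record fewer symptoms or SSIs under povidone-iodine.

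Tolerability is half of the purpose stated in 1.1, and SSI is the named secondary endpoint. Section 1.2 gives SSI results as the end goal of the wider programme. Section 6.3 provides for no safety monitoring that might pick up drift in either rating.

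**Working it through.** The plan gives no figure on this point, so the check is mainly a comparison of texts.

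1. *Who knows the arm?* At least the applier (1.9 A), and appliers are study investigators (1.7 B).
2. *Can an applier also rate?* Yes. The assistants help with both tasks (2.1), everyone is trained for both (2.2), and no rule stops a person doing both for one patient.
3. *Is arm withheld from the tolerability rater?* Section 1.3 B is silent on who rates and on masking.
4. *Is arm withheld from the SSI abstractor?* Sections 1.3 D and 6.4 A are silent. Section 6.2 limits access to identifiable data, and 4.7 E describes a password-protected spreadsheet. Neither describes a separate allocation record.
5. *Does the same gap reach the primary endpoint?* Not by this route. Section 1.8 A has the swabs enumerated by an outside facility, so the count does not rest on a team member's judgement.

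Steps 1 to 4 show that arm-aware rating is permitted. They do not show that it will happen.

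**How sensitive is the SSI rate to one reading?** The documents give no expected SSI rate for this trial, so 1% to 5% is assumed. Section 1.3 A plans 200 subjects in an approximately even ratio, about 200 / 2 = 100 per arm. Section 1.5 requires at least 85 per arm.

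Expected events per arm = n × rate. Relative change from one reclassified case = 1 / expected events.

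| Assumed rate | Events, n = 100 | Change from one case | Events, n = 85 | Change from one case |
|---|---|---|---|---|
| 1% | 1 | 100% | 0.85 | fewer than one event expected |
| 3% | 3 | 33% | 2.55 | 39% |
| 5% | 5 | 20% | 4.25 | 24% |

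Any rate built on so few events behaves this way, with or without bias. For scale, 3/100 against 2/100 gives a Fisher exact p of 1.0, so one case moves the reported rate without creating or removing a significant difference.

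No size is given for tolerability. The plan states no expected rate, no scale and no comparison for it.

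**The case against.** The strongest reply is that this is silence about who rates, not a plan for unblinded rating, and that little depends on it. Tolerability is in the aim but is neither a listed endpoint (1.3 D) nor an outcome measure (1.6 B), and it has no planned analysis (1.5, 6.1). SSI is secondary, was not used to size the trial, and has no stated between-arm test. The SSI finding comes from the surgeons' records, nothing says the surgeons know the arm, and an abstractor may only be transcribing a recorded diagnosis. Burning, pain and irritation are felt by the patient, so the patient's own masking matters as much as who asks. All of this stands, and it limits the weight of the point. It does not remove the point, because a stated aim and a named endpoint remain open to arm-aware rating that existing staff could largely avoid.

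A reader might also infer more than the documents support:

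- *That 6.2 shows abstractors know the arm.* It concerns patient identity and does not say that the identified dataset carries allocation.
- *That the applier asks the pre-operative tolerability questions.* No rater is named.
- *That SSI is judged from free-text notes.* The documents do not describe the form of the notes.
- *That nothing in the data could reveal misreading.* For SSI, antibiotic details are collected and could be cross-checked, and charts can be re-read by a masked reader. Tolerability answers cannot be taken again later.
- *That masking costs nothing.* It constrains the roster. The documents do not say whether the chart shows the pharmacy-dispensed product or whether the two solutions look alike.

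**Conclusion.** The concern holds as a gap in the safeguards: the plan permits people who know the arm to rate tolerability and to abstract SSI. It does not establish that they will, or that either result will be biased. The primary CFU endpoint is not affected by this.

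On an assumed SSI rate of 1% to 5% with 100 patients per arm, about 1 to 5 events are expected, and one case read differently changes an arm's rate by 20% to 100%. That range rests wholly on the assumed rate and measures fragility, not bias. The change should be made because it is cheap and protects a stated aim and the secondary endpoint. The main result does not depend on it.

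**What to change.** **Sections 1.3 D and 6.2 (SSI).** Hold allocation on a separate REDCap form that SSI abstractors cannot view, and keep it out of the spreadsheet described in 4.7 E. Have each chart abstracted by an existing team member who did not apply product to that patient. Make each SSI decision against one set of written criteria and lock it before arm is linked.

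**Section 1.3 B (tolerability).** Record tolerability as the patient's own report. Have the PACU questions asked by an existing team member who did not apply the product to that patient. State who asks in the pre-operative area and who, including the patient, is blinded.

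**Cost.** One access setting, a few sentences of protocol text and a small rostering constraint, with no change to treatment, visits or sample size. Section 1.3 C lets chart review run up to 4 months after the last procedure, so masked abstraction can still cover any chart not yet read.

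**Limits.** Masking of abstractors may be incomplete if the chart shows the study product; written criteria and locking still help in that case. In the pre-operative area the applier could still ask the questions, so there the protection rests on recording the patient's own report.

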6.3 Data and Safety Monitoring

[This section is required when research poses greater than minimal risk of harm to subjects.]

A. Data/Safety Monitoring Plan

N/A

B. Data/Safety Monitoring Board Details

N/A

6.4 Reporting Results

A. Individual Subjects' Results

Chart review of the electronic medical record will be used to follow up on patients' visits with their surgeons to determine presence or absence of surgical site infections at 7 and 30-day post-operative intervals.

B. Aggregate Results

Research results will not be shared with patients personally.

C. Professional Reporting

Results from the study will be written into a manuscript for submission into an academic journal and possibly presented at an appropriate medical conference to share results with the scientific community.

D. Clinical Trials Registration, Results Reporting and Consent Posting

A description of this clinical study will be available on ClinicalTrials.gov, as required by U.S. law.

6.5 Secondary Use of the Data

HRP-503a - TEMPLATE - Interventional Research Protocol 1.1.21
Protocol Title: Povidone-lodine for nasal decolonization

7.0 Research Repositories - Specimens and/or Data

N/A

8.0 Approvals/Authorizations

Uploaded

